### Data and Safety Monitoring

Because this is a minimal risk study involving only a telehealth-based intervention, we do not anticipate serious adverse events due to the study. However, safety information will be monitored at each interaction with the patient by the Interventionist via telephone sessions and the Research Assistants at outcome visits. All sites will be responsible for reporting SAEs to the PI in Durham as soon as the reporting individual becomes aware of the occurrence.

SAEs identified in Durham will be reported to the Durham PI who is responsible for complying with all cIRB reporting requirements. SAEs identified in Baltimore and Cleveland and Atlanta will be reported to their respective site-PI who will report all SAEs to the Durham PI who will report to cIRB, as required.

All adverse events will be reviewed by the Study PI, all four site-PIs (all of which are practicing MDs), the study statistician, and the project coordinator.

### **Safety Reasons that trigger immediate suspension of research**

Participants should normally be withdrawn from the trial if a serious adverse event (SAE) occurs. Participants must be withdrawn from the trial if:

- a. They withdraw their consent
- b. Veteran subsequently meets one of the exclusion criteria for the study.
- c. The investigator considers it in the best interest of the veteran that he or she is withdrawn.
- d. Veteran displays abusive behavior towards staff
- e. Veteran is a female and become pregnant during the study
- f. The study is suspended or cancelled

The reason and date of withdrawal will be documented by research staff in the study tracking database. For patients in the intervention arm who no longer want to participate in the intervention, they will still be eligible to complete the outcome assessments (at months 4, 8, 12) and receive payment for completion of those visits.

The Durham PI will be responsible for reporting to the VA Central IRB within 5 business days any SAEs that meet the criteria, as well as any follow-up reports requested. Summary information that did not require immediate reporting will be submitted at continuing review.

The PI/SC will ensure adequate monitoring in the following ways: all study staff will have completed their required research training prior to beginning any research activity, ensuring that each member of the research team has a research scope of practice (SOP), updated annually, that clearly defines the duties in which the person is trained, qualified and allowed to perform for research purposes, and will maintain a staff listing of all personnel involved in the conduct of the study which will include their CITI and GCP training completion dates.

All non-compliance with the study protocol will be reported. Protocol deviations or protocol violations will be reported to the cIRB by the Durham PI within 5 business days after being made aware of the occurrence using Form 119 if initiated in response to an SAE or UAP, or Form 129 if the event was likely to have an adverse effect on the subjects rights, safety or welfare, their willingness to continue participation, or the integrity of the research data.

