**Intervention contacts:** Participants randomized to the intervention will receive a video call from the interventionist within 2-5 days of enrollment. While connected via video (using VVC) with the Veteran, the interventionist will conduct a medication assessment, including participant's knowledge of the purpose and side effects of each BP or cholesterol medication and current or potential adherence strategies. If the Veteran or Interventionist is unable or unwilling to use VVC, these contacts may also be conducted by telephone. Telephone calls may be recorded for quality control purpose only (no name will be captured on the recording, and consent would be obtained prior to any recording). At a minimum, the interventionist will have contacts at 0, 2, 4, 6, 8, 10 and 12 months (see figure 4). An initial 2-week follow-up call will ensure proper use of the home BP monitor and to address any other questions. Prior to each interventionist contact, similar to prior studies, we will request home BP values for the past two weeks using ANNIE SMS, with the goal of using the average of at least 3 values to determine BP control. For veterans unable/unwilling to use Annie, we can collect the home BP measurements over

**Figure 4:** Example scenarios of intervention participant contact frequency. (A) Participant with lower intensity requirements; (B) Participant with higher intensity requirement; (C) Control participant. Squares represent in-person visits and outcome assessment time points, Triangles represent Virtual visits and lines are telephone contact.

the phone or by secure messaging to the interventionist. In addition, the interventionist will contact the intervention subjects at up to 2-week intervals as necessary to carry out the multi-component intervention. Frequency of contact will be determined by whether the participant remains above goal BP or is initiating new treatments (e.g. starting another BP medication). Regardless of contact, study outcomes are collected routinely at the same frequency for both arms.

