## 5.7 Withdrawal of Subjects

**Participant withdrawal.** Because this is a minimal risk study, it is unlikely subjects will be withdrawn due to safety concerns. Participants are free to withdraw from the study at any time for any reason. However, the study team will meet weekly to determine cumulative enrollment and drop-out rates, as well as charts of these rates over time so that we can detect any changes. Any individuals who decline to participate or drop out of the study will be asked to describe a specific reason for this choice. These reasons will be tracked in the study database. We will regularly review the numbers of patients who cite different reasons for refusal / drop-out, and if there are any factors that can be modified in our study approach, we will take action as appropriate. The project coordinator will also present, at each meeting, enrollment and drop-out rates according to gender, race, and clinic. If any differences are observed, we will examine refusal / drop-out reasons endorsed by these different groups to detect whether there are any systematic study-related processes that may be influencing these differences.

**Investigator withdrawal:** Participants should normally be withdrawn from the trial if a serious adverse event (SAE) occurs. The below are the reasons an investigator may withdraw a participant from the study.

1. The investigator considers it in the best interest of the veteran that they or she is withdrawn
2. A Veteran displays abusive behavior towards staff
3. A patient is female and becomes pregnant during the study
4. The study is suspended or cancelled

The reason and date of withdrawal will be documented by research staff in the study tracking database. For patients in the intervention arm who no longer want to participate in the intervention, they will still be eligible to complete the outcome assessments (at months 4, 8, 12) and receive payment for completion of those visits.

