## 5.0 Reporting

### ***Unexpected and serious adverse event reporting:***

Because this is a minimal risk study involving only a telehealth based intervention, we do not anticipate serious adverse events due to the study. However, safety information will be monitored at each interaction with the patient by the Interventionist via telephone sessions and the Research Assistant at outcome visits. Specific information regarding safety collected during telephone calls and visits with the research assistants will be summarized for reporting. Due to the age range and health conditions (HIV, hypertension, hyperlipidemia, cardiovascular disease, physical inactivity, smoking) of the patients identified for participation in the study, hospitalizations and other health events, including diagnosis of new medical conditions, surgeries, ER visits, MI, Stroke, falls and death, unrelated to the study are expected. Any events that fall into one of these categories will be reported at continuing review. Additionally, we expect that some patients may be uncomfortable answering survey questions or have pain and bruising as a result of blood draw for labs, which is similar to usual medical care. It is also expected that participants will miss monthly phone calls during the required time window and we will not consider either of these events protocol deviations. A study physician will be on call at all times at their site. There will not be a data monitoring committee for the study. The PI, site PIs, study Statistician, and project coordinator will serve this role. All adverse events will be reviewed by the PI and Site PIs, the study statistician, and the project coordinator. All sites will be responsible for reporting SAEs to the PI in Durham as soon as the reporting individual becomes aware of the occurrence. Durham will be responsible for conveying information from each site to the VA Central IRB. The VA Central IRB Table of Reporting Requirements will be used to guide all of our reporting decisions, with time windows given for each type of report.

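### The withdrawal rules take participants out of the trial after an SAE or a later exclusion condition, with no provision for continued SBP visits, and the protocol's two withdrawal sections disagree

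*Protocol*

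**What the plan says.** The same SAE sentence stands in Protocol 5.7 and in the safety section of the Communication Plan (Safety Reasons that trigger immediate suspension of research): "Participants should normally be withdrawn from the trial if a serious adverse event (SAE) occurs". The two lists that follow it differ.

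- The safety section lists conditions under which withdrawal *must* happen. Item b is "Veteran subsequently meets one of the exclusion criteria for the study".
- Section 5.7 introduces its list with "The below are the reasons an investigator may withdraw a participant from the study". It has no counterpart to item b, and it opens by saying that "it is unlikely subjects will be withdrawn due to safety concerns".

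The exclusion criteria (Protocol 5.4 and SAP) include hospitalisation for CABG, MI or stroke in the last 90 days. The adverse-event reporting section expects MI, stroke and hospitalisation in this population. The nursing-home exclusion adds that people are censored on entry. Neither document defines that word for the SBP model.

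Continued assessments are written down for one group only, in identical words in both sections: "For patients in the intervention arm who no longer want to participate in the intervention, they will still be eligible to complete the outcome assessments". Against this, Protocol 5.1 (Intervention contacts) says: "Regardless of contact, study outcomes are collected routinely at the same frequency for both arms".

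The SAP specifies an intention-to-treat mixed model on all available data. It drops medical-record SBP as a fallback for missing values.

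**The concern.** An SAE or a new cardiovascular admission is a reason to reconsider the intervention. It is not in itself a reason to stop measuring the primary outcome. The protocol draws this distinction for people who tire of the intervention, but not for people who have an event, and not for the control arm.

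Three things are at stake. First, a literal reading loses post-event SBP in people whose health has just changed, and an intention-to-treat analysis should want those values. Second, nothing in the analysis tests what that loss does. Both documents describe missing at random in terms of treatment, prior outcome and baseline covariates, and the SAP's imputation model adds only baseline characteristics. No planned analysis departs from that assumption. Third, four sites could treat the same MI differently, depending on which section they follow.

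The rules cover both arms, but the study may learn of events on different schedules. The protocol says "safety information will be monitored at each interaction with the patient by the Interventionist via telephone sessions and the Research Assistant at outcome visits". For the intervention arm, "At a minimum, the interventionist will have contacts at 0, 2, 4, 6, 8, 10 and 12 months"; control participants have only the visits at 0, 4, 8 and 12 months. Equal event rates therefore need not give equal withdrawal.

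**Working it through.** **1. The texts side by side**

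| Question | Safety section | Section 5.7 | Elsewhere in the protocol |
|---|---|---|---|
| After an SAE | Normally withdrawn | Same sentence, but safety withdrawal called unlikely | Reporting section sends expected events to continuing review and does not mention withdrawal |
| Exclusion criterion met later | Must be withdrawn | Not listed | Section 5.1 lets a provider take a patient off the medication protocol, for instance after a recent ASCVD event, while the rest of the intervention continues; the risk section gives a similar option |
| Outcome visits afterwards | Only for intervention patients who no longer want it | Same | Section 5.1: collected at the same frequency in both arms regardless of contact |

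**2. The plan's power figure**

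Inputs (Protocol 5.6, Power): 300 participants at 1:1, SD 17, within-person correlation 0.4, 15% missing at 12 months, 6 mmHg, two-sided 0.05.

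Hand check: SE ≈ 17·√(1−0.4²)·√(2/(150·0.85)) = 15.58·0.1252 = 1.95. Power = Φ(6/1.95 − 1.96) ≈ 0.87. The generalised-least-squares standard error for the common-intercept model, with losses of 5%, 10% and 15%, is 1.941, giving power 0.871. The plan's claim of more than 80% is confirmed.

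| 12-month loss | 15% | 20% | 25% | 30% | 31% | 32% |
|---|---|---|---|---|---|---|
| SE (mmHg) | 1.941 | 1.996 | 2.057 | 2.125 | 2.139 | 2.154 |
| Power | 0.871 | 0.852 | 0.831 | 0.806 | 0.801 | 0.796 |

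**3. Bias if one arm loses more (illustrative)**

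Assumed, because the documents give no values: an extra share q = 5-10% is withdrawn in one arm, and those people's SBP differs by D = 10 mmHg. Under the planning correlation ρ = 0.4, k observed visits recover a fraction w = kρ/(1+(k−1)ρ) of a shift present at every visit, so w = 0.400, 0.571, 0.667 for k = 1, 2, 3.

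- Shift present from baseline: bias = q·D·(1−w). For q = 5%: 0.30, 0.21, 0.17 mmHg. For q = 10%: 0.60, 0.43, 0.33 mmHg.
- Shift that begins after the last observed visit: earlier visits carry no information on it, so bias = q·D = 0.50 to 1.00 mmHg.
- Equal withdrawal of 5-10% with the shift in one arm only: again 0.50 to 1.00 mmHg.
- Equal withdrawal and equal shifts: 0.

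The largest value is 1.00/1.94 = 0.52 of a standard error, or 1.00/6 = 17% of the target effect.

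**4. Contact schedules alone (illustrative)**

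Assumed: the same event rate e = 10-20% in both arms, events uniform over 12 months, every event leading to withdrawal at the next contact (2-monthly against 4-monthly), and a 10 mmHg shift from the event onward.

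- *SBP at the visit where the event is learnt is kept.* The 12-month value is lost for events in months 0-10 in the intervention arm and months 0-8 in control. Loss is e·10/12 against e·8/12: 8.3% against 6.7% at e = 10%, and 16.7% against 13.3% at e = 20%. Least squares gives a bias of 0.26 and 0.54 mmHg.
- *That SBP is not kept.* Each event then removes the same visits in both arms, and the bias is 0.

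The documents do not say which applies.

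**The case against.** The best case for the plan is that this is loose template wording. No passage says that outcome visits stop, *normally* leaves discretion, and safety withdrawal is called unlikely. The passages on outcome collection, medication-protocol removal and event reporting all suggest that a patient with an MI was meant to stay in. The 15% loss allowance matches 80-88% retention in earlier studies and may already include such withdrawals. Reasons and dates of withdrawal are recorded, baseline differences by retention will be tested, and a STROBE or CONSORT figure is listed.

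Much of this stands, and it rules out stronger readings. A reader might infer that post-event SBP will certainly be lost; that is the literal reading of withdrawal from the trial, but not a stated instruction. A reader might infer that missing at random is breached or that the result will favour the intervention; the documents show neither, and an event outside the model does not by itself breach the assumption. The sign depends on which arm loses more and on whether withdrawn patients run higher or lower. Nor is the trial made underpowered.

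The objection does not remove item b. It is mandatory, it names no exception for outcome visits, and the passages in tension with it do not override it. The planned baseline comparisons also do not test dependence on unobserved SBP.

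**Conclusion.** The concern holds as a defect in the follow-up rules and an inconsistency between two sections. It does not demonstrate bias. Followed literally, the rules discard obtainable post-event SBP, contrary to the intention-to-treat aim, and the SAP has no analysis that would show the consequence. Censoring at nursing-home entry has no meaning for a repeated-measures SBP model.

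The size of any bias cannot be derived from the documents. Under the assumptions above it runs from zero, when withdrawals and shifts are alike by arm, to about 1 mmHg. Contact schedules alone give 0 to about 0.5 mmHg. Power stays at 80% or more up to about 31% loss. This should be fixed because prevention is cheap. Confidence is medium, since event rates, arm gap and SBP shift are all assumed.

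**What to change.** Use one withdrawal list in section 5.7 and the safety section. State that an SAE, a later exclusion condition or nursing-home entry may stop the intervention but does not by itself end the 4-, 8- and 12-month SBP and lipid assessments, in either arm. Allow three exceptions: consent for follow-up is withdrawn, decision-making capacity is lost without an approved consent route, or the investigator judges assessment to be against the participant's interest. Delete the censoring wording for SBP, and keep every measured value in the intention-to-treat model.

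For participants already withdrawn, or if follow-up has closed, report withdrawals by arm, reason and timing from the tracking database. Add a delta-adjusted sensitivity analysis that shifts their imputed 12-month SBP by −10 to +10 mmHg, separately by arm.

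The cost is a central-IRB amendment, a few lines of SAP text and a small extra analysis. The visits and payments are already planned. The documents do not say whether follow-up was still open at the June 2025 SAP revision; if it had closed, only the reporting and the delta analysis remain.

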Statistical Analysis Plan

Project: A nurse-led intervention to extend the Veteran HIV treatment cascade for cardiovascular disease prevention (V-EXTRA-CVD)

Principal Investigators: [name] PhD

Deliverable (e.g., manuscript, report): Manuscript

Statistical Analysis Plan

Project: A nurse-led intervention to extend the Veteran HIV treatment cascade for cardiovascular disease prevention (V-EXTRA-CVD)

NCT04545489

Principal Investigator: [name] PhD

Creation Date: November 17, 2024

Revision Date: June 6, 2025

Deadlines: End of funding

Deliverable (e.g., manuscript, report): Manuscript

Some of these are specific to clinical trials (based on this [JAMA paper](#)) and some are other are specific to observational studies (based on [STROBE/RECORD](#) guidelines),

Statistical Analysis Plan

Project: A nurse-led intervention to extend the Veteran HIV treatment cascade for cardiovascular disease prevention (V-EXTRA-CVD)

Principal Investigators: [name] PhD

Deliverable (e.g., manuscript, report): Manuscript

Study Overview:

The VA is the largest provider of HIV care in the United States. The ~31,000 Veterans with HIV use significantly more healthcare and have up to 2x higher risk of atherosclerotic cardiovascular disease (ASCVD) compared to uninfected Veterans. The HIV treatment cascade model includes care steps; once people obtain remission, providers should focus on preventing ASCVD. We will extend the HIV treatment cascade and focus on reducing ASCVD risk among people with HIV. Veterans with HIV have low perceived risk for ASCVD and uptake of guideline-based treatment for BP is low.

Study Aims:

Aim 1: Conduct a formative evaluation to adapt intervention.

Aim 1a: Conduct qualitative interviews with Veterans with HIV and Providers to ascertain perceptions regarding CVD risk reductions to inform intervention adaptation.

Aim 1b: Adapt the intervention to the VA HIV clinic context with key stakeholder input.

Aim 1c: Conduct a retrospective review of the nationwide cohort of Veterans with HIV to evaluate hypertension care in order to inform needs for the study.

Aim 2: Evaluate the 12-month *efficacy* of an intervention to improve systolic blood pressure in Veterans with HIV.

Aim 3: Conduct an evaluation of the prevention intervention.

Exploratory aim: If effective, we will conduct a budget impact analysis and simulate 10-year cost-effectiveness of the intervention.

Study Hypotheses:

We hypothesize that our intervention will result in a clinically significant 6mmHg reduction in SBP and 15 mg/dL improvement in non-HDL cholesterol over 12 months compared to those receiving [*enhanced education + usual care*] only.

Primary Hypotheses:

Null hypothesis is mean SBP at 12 months will be the same between the intervention and control arms:

$H_0: \mu_1 = \mu_2$

Alternative hypothesis is mean SBP at 12 months will be different in the intervention arm (μ_1) as compared to the control arm (μ_2):

$H_a: \mu_1 \neq \mu_2$

Secondary Hypotheses:

Null hypothesis is mean non-HDL cholesterol at 12 months will be the same between the intervention and control arms:

$H_0: \mu_1 = \mu_2$

Alternative hypothesis is mean non-HDL cholesterol at 12 months will be different in the intervention arm (μ_1) as compared to the control arm (μ_2):

$H_a: \mu_1 \neq \mu_2$

Some of these are specific to clinical trials (based on this [JAMA paper](#)) and some are other are specific to observational studies (based on [STROBE/RECORD](#) guidelines),

Statistical Analysis Plan

Project: A nurse-led intervention to extend the Veteran HIV treatment cascade for cardiovascular disease prevention (V-EXTRA-CVD)

Principal Investigators: [name] PhD

Deliverable (e.g., manuscript, report): Manuscript

Study Design:

We will conduct qualitative interviews with care team and Veterans to adapt the intervention in an iterative design process. We will then conduct a RCT to evaluate an intervention to reduce ASCVD risk. The study will be conducted in 4 clinics among HIV+ veterans ($n=300$) on suppressive ART with confirmed SBP >140 mmHg, stratified by clinic site and hyperlipidemia status and randomized 1:1 to intervention vs. education control. The intervention will involve 4 evidence-based components based on our prior studies and adapted to veterans with HIV: (1) interventionist-led care coordination, (2) interventionist-managed medication and adherence support (3) home BP monitoring, and (4) administered VA Video Connect (VVC). The education control will receive enhanced education and usual care. Primary outcome: difference in 12-month systolic BP in the intervention arm vs control. Secondary outcome: 12-month difference in non-HDL cholesterol. We will use a mixed-methods design to evaluate fidelity, dose delivered/received, reach, recruitment, and context of the intervention.

Study Population:

We plan to enroll 300 HIV+ Veterans who are on suppressive ART with **HIV-1 RNA <200 copies/ml** checked at least twice within the prior year if they have hypertension and receive care at the 4 clinic sites. Our plan is to enroll approximately 100 from each of the following sites the Durham VA Healthcare System, Cleveland VA Healthcare system, Baltimore VA HealthCare System and the Atlanta VA Healthcare System. We may enroll more or less at the different sites depending on acceptance of study at the sites. Since site is one of our randomization strata enrolling more at one site will not impact analysis. Additionally, while 300 is our enrollment goal, we may consent and randomize up to 310, to account for site differences, withdrawals and the scheduling availability and preferences of Veteran participants.

Inclusion Criteria:

Variable	Description	Variables and Source	Specifications
1. Age \geq 18 years 2. Confirmed HIV+ diagnosis 3. Undetectable HIV viral load: defined as the most recent HIV viral load < 200 copies/mL, checked within the past 18 months (assessed via chart abstraction) 4. Hypertension: defined as having 2 recent outpatient BP measurements in the last 18 months to show systolic BP ≥ 130 and/or diastolic ≥ 90 mmHg OR being prescribed anti-hypertensive medication (assessed via chart abstraction) 5. Veteran at one of the sites participating in the study sites			

Some of these are specific to clinical trials (based on this [JAMA paper](#)) and some are other are specific to observational studies (based on [STROBE/RECORD](#) guidelines),

Statistical Analysis Plan

Project: A nurse-led intervention to extend the Veteran HIV treatment cascade for cardiovascular disease prevention (V-EXTRA-CVD)

Principal Investigators: [name] PhD

Deliverable (e.g., manuscript, report): Manuscript

Exclusion Criteria:

Variable	Description	Variables and Source	Specifications

1. Severely hearing or speech impaired, or other disability that would limit participation2. In a nursing home at baseline and/or any long-term care facility. Individuals will be censored at the point of entering nursing home care3. In-patient psychiatric care4. Diagnosis of dementia or active psychosis5. Terminal illness with life expectancy < 4 months (ex. Metastatic cancer, Hospice care,)6. Recent (<90day) hospitalization for CABG, MI, stroke)7. Pregnant, breast-feeding, or planning a pregnancy during the study period8. Planning to move out of the area in the next 12 months.9. No reliable access to telephone services10. Currently enrolled in a competing research study (e.g. an intervention that may impact BP management)			

Some of these are specific to clinical trials (based on this [JAMA paper](#)) and some are other are specific to observational studies (based on [STROBE/RECORD](#) guidelines),

Statistical Analysis Plan

Project: A nurse-led intervention to extend the Veteran HIV treatment cascade for cardiovascular disease prevention (V-EXTRA-CVD)

Principal Investigators: [name] PhD

Deliverable (e.g., manuscript, report): Manuscript

Treatment Group:

Description	Variables and Source	Specifications
Intervention	REDCap instrument [enrollment_and_randomization] and variable [studyarm]	1 = Education Control 2 = V-EXTRA-CVD Intervention

Comparison Group:

Description	Variables and Source	Specifications
Education control group	REDCap instrument [enrollment_and_randomization] and variable [studyarm]	1 = Education Control 2 = V-EXTRA-CVD Intervention

Primary Outcomes:

Outcome	Description	Variables and Source	Specifications
Systolic Blood Pressure at 12 months	Systolic blood pressure	All BPs used for outcomes will be obtained by a research assistant and entered into REDCap survey systolic	Continuous

Secondary Outcome:

Outcome	Description	Variables and Source	Specifications
Non-HDL Cholesterol at 12 months	Non-HDL cholesterol	All cholesterol levels used for outcomes will be obtained by a research assistant and entered into REDCap survey nonhdl	Continuous

Some of these are specific to clinical trials (based on this [JAMA paper](#)) and some are other are specific to observational studies (based on [STROBE/RECORD](#) guidelines),

Statistical Analysis Plan

Project: A nurse-led intervention to extend the Veteran HIV treatment cascade for cardiovascular disease prevention (V-EXTRA-CVD)

Principal Investigators: [name] PhD

Deliverable (e.g., manuscript, report): Manuscript

Covariates for Descriptive, Matching or Regression Purposes:

Stratification Variables:

Variable	Description	Variables and Source	Specifications
Site	Site where Veteran was randomized; stratification variable	REDCap: site	Atlanta, Baltimore, Cleveland, Durham
Hyperlipidemia	Hyperlipidemia status at randomization; stratification variable	REDCap: HYPERLIPIDEMIA_2	0 = No Hyperlipidemia 1 = Hyperlipidemia

Descriptive Clinical Outcomes:

Outcome	Description	Variables and Source	Specifications
SBP	Baseline 4m 8m 12m	Long: systolic Wide: systolicbase, systolic4, systolic8, systolic12	Continuous
DBP	Baseline 4m 8m 12m	Long: diastolic Wide: diastolicbase, diastolic4, diastolic8, diastolic12	Continuous
Non-HDL Cholesterol	Baseline 4m 8m 12m	Long: Nonhdl Wide: nonhdlbase, nonhdl4, nonhdl8, nonhdl12	Continuous
Cholesterol	Baseline 4m 8m 12m	Wide: choltotalbase, choltotal4, choltotal8, choltotal12	Continuous
HDL	Baseline 4m 8m 12m	Long: hdl Wide: hdlbase, hdl4, hdl8, hdl12	Continuous
LDL	Baseline 4m 8m 12m	Long: ldl Wide: ldlbase, ldl4, ldl8, ldl12	Continuous

Some of these are specific to clinical trials (based on this [JAMA paper](#)) and some are other are specific to observational studies (based on [STROBE/RECORD](#) guidelines),

Statistical Analysis Plan

Project: A nurse-led intervention to extend the Veteran HIV treatment cascade for cardiovascular disease prevention (V-EXTRA-CVD)

Principal Investigators: [name] PhD

Deliverable (e.g., manuscript, report): Manuscript

Other Variables:

Variable	Description	Variables and Source	Specifications
ID		Record_id	
Sex		Demog_sex	1 = Male 2 = Female
Gender		DEMOG_GENDER	1 = Man 2 = Woman 4 = Transgender Woman
Sexual orientation		SEXUALORIENTATION	0 = Other 1 = Heterosexual
Race		RACE	0 = White 1 = Black or African American 2 = Other
Ethnicity		DEMOG_HISPANIC	1 = Yes 2 = No 3 = Don't Know
Education		EDUCATION	1 = High school or less 2 = Some college or trade school 3 = College graduate or higher
Employment Status		EMPLOYMENT	0 = Employed 2 = Unemployed 3 = Retired
Marital Status		MARRIED	0 = Not married 1 = Married 2 = DK/Missing
Financial Status		FINANCIAL	0 = No financial troubles 1 = Financial troubles
Housing or Food Insecurity		HOUSEFOODINSECURE	0 = No housing or food insecurity 1 = Housing or food insecurity
Rurality		GISURH	H = Rural R = Rural U = Urban
Smoking Status		SMOKINGSTATUS_2	0 = Never smoker 1 = Current smoker 2 = Prior smoker
Age		AGE	Continuous
Time since HIV diagnosis	In years	HIVDX_YEARS	Continuous
10-year ASCVD risk score		ASCVDRISK_10YR	Continuous
Lifetime ASCVD risk score		ascvdrisk_lifetime	Continuous

Some of these are specific to clinical trials (based on this [JAMA paper](#)) and some are other are specific to observational studies (based on [STROBE/RECORD](#) guidelines),

Statistical Analysis Plan

Project: A nurse-led intervention to extend the Veteran HIV treatment cascade for cardiovascular disease prevention (V-EXTRA-CVD)

Principal Investigators: [name] PhD

Deliverable (e.g., manuscript, report): Manuscript

ASCVD risk category	<20 (low risk - reference) and >=20 (high risk)	Ascvd_risk_cat	0 = Low risk 1 = High risk
ADI national rank		ADI_NATRANK	Continuous
ADI state rank		ADI_STATERNK	Continuous
Chaos total score		CHAOSTOTAL	Continuous
Loneliness total score		LONELYTOTAL	Continuous
“Out of control” baseline SBP	Baseline SBP \geq 140	SYSTOLICGTE140	0 = No 1 = Yes

Statistical Plan:

Primary Analysis:

The primary outcome will be systolic BP at 12 months and secondary outcome will be non-HDL cholesterol at 12 months, both measured at 4 time-points (0, 4, 8, and 12 months). All BPs used for outcomes will be obtained by a research assistant and cholesterol levels will be measured by lab personnel who are also blinded to treatment group. Because the outcomes are continuous, linear mixed-effects models⁷⁹ (LMM) will be used to examine the differences over time between the study arms. LMM will allow us to implicitly account for the correlation between a patient's repeated measurements over time. The general mean structure of the LMM we will use to examine the hypotheses is:

$$Y_{ij} = \beta_0 + \beta_1 * I(month = 4) + \beta_2 * I(month = 8) + \beta_3 * I(month = 12) + \beta_5 * arm * I(month = 4) + \beta_6 * arm * I(month = 8) + \beta_7 * arm * I(month = 12) + \beta_8 * clinic + \beta_9 * hyperlipidemia$$

where Y_{ij} represents the outcome of interest (i.e., SBP or non-HDL) for patient i at time j . We will fit a common intercept and arm is the intervention group indicator. Similarly, time will be classified, where for example, $I(month = 12)$ is a dummy variable equal to 1 for the 12 month time point. Random intercepts will be included for each individual to account for correlation among repeated measurements over time. The primary analytic model will adjust for clinic site (reference: Durham) and hyperlipidemia status. The mixed effects model parameters will be estimated and tested using SAS PROC MIXED (SAS Institute, Cary, NC), and the hypothesis of between-arm differences over time will be tested using estimate statements within PROC MIXED. In particular, β_7 , the estimated difference in outcome between arms at 12 months, will be the primary effectiveness outcome assessed. All analyses will be conducted following an intention to treat (ITT) principle using all available data.

We will examine the observed trajectories of outcome measurements over time to determine if the overall slope is also of interest.

Update 5/9/2025: instead of using a random intercept for each person (which essentially assumes a CS covariance structure), we will use a repeated statement with an unstructured covariance matrix. This is more flexible than CS and works well with a limited number of time points.

Secondary Analyses:

The secondary outcome will be non-HDL cholesterol at 12 months and use the same model structure listed in the primary outcome section.

Some of these are specific to clinical trials (based on this [JAMA paper](#)) and some are other are specific to observational studies (based on [STROBE/RECORD guidelines](#)),

Statistical Analysis Plan

Project: A nurse-led intervention to extend the Veteran HIV treatment cascade for cardiovascular disease prevention (V-EXTRA-CVD)

Principal Investigators: [name] PhD

Deliverable (e.g., manuscript, report): Manuscript

Update 5/28/2025: Since hyperlipidemia is strongly correlated with cholesterol, this term has been omitted from the models with non-HDL cholesterol as the outcome. While including randomization stratification variables can help with precision, it is better to omit this variable from these models.

Sensitivity Analysis/Missing Data:

We will assess mechanisms for missing data in this study. LMM implicitly accommodates missingness when the response is Missing At Random (MAR); that is, when missingness is due either to treatment, to prior outcome, or to other baseline covariates included in the LMM.

Our primary analysis will include all available study-collected data. We will first examine the amount of missingness at each timepoint for each of the two outcomes. We may impute missing values using multiple imputation procedures as described by Schafer. Each imputed dataset will be analyzed with the LMM model, and final parameter estimates and their standard errors will be calculated using Rubin's formula.

Notes on the protocol: The original protocol specified the following plan to fill in missing data (doing this process separately for each outcome):

1. Use all available study-reported data
2. If missing study-reported value, use the SBP or non-HDL cholesterol value if available in the EMR in a 2-month window from the target data for that time point.
3. If missing EMR-reported value, assess whether the outcome has >10% missing remaining
 - a. If yes, $\geq 10\%$ missing, use multiple imputation
 - b. If no, $<10\%$ missing, do not use multiple imputation, include only study- and EMR-reported values.

Updated plan: We will not plan to use EMR data for SBP due to concerns about the consistency of these measurements in different settings. For example, SBP may vary, with lower values observed in calmer settings. On the other hand, non-HDL cholesterol may be more consistent which could allow us to use EMR data. In addition, we will not use 10% as a strict threshold for imputation as it is unclear if this is 10% missing at each time point or overall. We will instead examine if characteristics vary by retention status at each time point. For example, there may be variables highly related to missingness but <10% missingness; in such a case, we may still want to impute missing values. Any baseline characteristic found to be associated with missingness at any time point will be included in the imputation model.

Attrition bias: As part of our examination of missing data, we will assess differences in baseline characteristics (e.g., clinic site, demographics, clinical values, medical history) by retention at each follow up time point. We will use two sample t-tests (or Wilcoxon rank sum tests) for continuous variables and chi-squared tests (or Fisher's exact test) for categorical variables.

Subgroup Analyses:

Pre-specified sub-group analyses of the primary and secondary outcomes will include clinic site (reference: Durham), sex (reference: male), and baseline ASCVD risk category (<20%, $\geq 20\%$) (reference: low risk). For each category, we will examine the interactions with intervention arm and time. Generally, the modeling approach will mirror that described above for each outcome. Three separate analyses for each outcome will be conducted to assess the effect of each potential moderator. Models will be fit in SAS PROC MIXED, as described above, and the moderating effect of each of the three factors will be assessed via the hypothesis test of the three-way interaction among subgroup, treatment, and time at 12 months. We may also report the results for time at 4 months and time at 8 months if this is of interest.

Some of these are specific to clinical trials (based on this [JAMA paper](#)) and some are other are specific to observational studies (based on [STROBE/RECORD guidelines](#)),

Statistical Analysis Plan

Project: A nurse-led intervention to extend the Veteran HIV treatment cascade for cardiovascular disease prevention (V-EXTRA-CVD)

Principal Investigators: [name] PhD
Deliverable (e.g., manuscript, report): Manuscript

An example model for sex is as follows, with the addition of the main effect for sex, interactions between sex and study visit, and interactions between sex, study visit, and treatment arm.

$$Y_{ij} = \beta_0 + \beta_1 * I(month = 4) + \beta_2 * I(month = 8) + \beta_3 * I(month = 12) + \beta_5 * arm * I(month = 4) + \beta_6 * arm * I(month = 8) + \beta_7 * arm * I(month = 12) + \beta_8 * clinic + \beta_9 * hyperlipidemia + \beta_{10} * sex + \beta_{11} * I(month = 4) * sex + \beta_{12} * I(month = 8) * sex + \beta_{13} * I(month = 12) * sex + \beta_{14} * arm * I(month = 4) * sex + \beta_{15} * arm * I(month = 8) * sex + \beta_{16} * arm * I(month = 12) * sex$$

Additional Analyses:

We decided to add additional, post-hoc analyses examining the moderating effects of “out of control” baseline SBP (baseline SBP \geq 140) and race. The same approach from the subgroup analysis section will be used here.

